Calcium also has a positive inotropic effect both on skeletal muscle and smooth muscle. The inotropic effect doesn't skip the myometrium, and it is well-established that hypocalcemia can impair myometrial contractility [12], [13]. As so, calcium channel blockers are prescribed as a tocolytic drug and calcium gluconate should be considered as adjuvant therapy for treating PPH duo to atony, in case of prolonged tocolytic or magnesium sulfate use prior to delivery [14]. Studies have already shown an association between low ionized calcium levels and the risk for severe bleeding. In one study, the rate of hypocalcemia was 10.6% in patients with non-severe PPH and 51.5% in patients with severe PPH [15]. Furthermore, in a pilot randomized controlled trial of patients with risk factors for uterine atony, calcium was shown to reduce uterine atony compared to placebo [16]. However, current studies have small sample size and are limited to a high-risk population. Although it is acknowledged that hypocalcemia combined with acidosis and hypothermia contribute to worsening coagulopathy and increased morbidity in PPH [2], there are no recommendations in current guidelines for monitoring calcium levels or prescribing calcium as a prophylactic measure for the third stage of labor [15], despite atony and coagulopathy being significant causes of PPH.

Co-administration of calcium and oxytocin was examined in previous study, and there were no changes in maternal hemodynamics [17].

HYPOTHESIS

Administration of Calcium Gluconate at the third stage of elective Cesarean delivery will decrease the rates of blood loss during and after the surgery by reducing the rates of uterine atony and development of coagulopathy, thus has the potential of reducing the incidence of PPH and its complications without severe side effects.

RESEARCH QUESTIONS

Primary research question

Population (P), Intervention (I), Comparison (C), Outcome (O)

- P: All women undergoing elective cesarean delivery.
- I: Administration of Calcium Gluconate 10% IV following umbilical cord clamping.
- C: Administration of normal saline 0.9% IV following umbilical cord clamping.
- O: Decreased mean hemoglobin drop after cesarean delivery.

Outcome measures

Primary outcome:

.1 Decreased mean hemoglobin drop after cesarean delivery at the Calcium gluconate arm, compared to the control arm.

Secondary outcome:

- 1. The rate of women with a decrease of hemoglobin levels of 2 gr/dl or more.

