An ECG strip will be done prior to the surgery, making sure that the patient doesn't suffer from a QT segment abnormality.

All patients will be monitored with a 3 lead- ECG prior, during, and 2 hours following calcium administration. Patients with QT interval abnormalities will be excluded from the trial.

After the surgery, a blood sample will be drawn and sent to blood gas analysis (determining ionized calcium levels) and for coagulation profile. A complete blood count will be routinely taken for all women the next day. The hemoglobin level will be compared to the hemoglobin level prior to CD.

ANALYSIS PLAN

Binyamin Y et al. demonstrated an average blood loss of 1.05 g/dL in 1000 women who have had a cesarean delivery for different indications[17]. Assuming a reduction in blood loss of 30% attributed to both coagulative effect and uterotonic effect of Calcium, and calculating a dropout rate of 10%, a sample size of 1180 patients (590 in each arm) is needed to achieve power of 0.8 and p-value <0.05. We will use SPSS 28 (IBM inc.) for statistical analysis. Categorical variables will be compared using the chi-square test or fisher's exact test. Continuous variables will be compared using the student's t-test or Mann-Whiteny test. After testing for collinearity, confoundment and interaction, a multivariate model will be built to assess the effect of calcium supplementation on postpartum hemorrhage. Alpha < 0.05 is considered statistically significant.

References:

- C. Deneux-Tharaux, M.-P. Bonnet, and J. Tort, "[Epidemiology of post-partum haemorrhage].," J Gynecol Obstet Biol Reprod (Paris), vol. 43, no. 10, pp. 936–50, Dec. 2014, doi: 10.1016/j.jgyn.2014.09.023.
- [2] "Postpartum Hemorrhage ACOG PRACTICE BULLET IN Clinical Management Guidelines for Obstetrician-Gynecologists," 2017. [Online]. Available: http://www1.health.nsw.gov.au/pds/ActivePDSDocuments/
- [3] L. Sentilhes, F. Goffinet, C. Vayssière, and C. Deneux-Tharaux, "Comparison of postpartum haemorrhage guidelines: discrepancies underline our lack of knowledge," *BJOG*, vol. 124, no. 5, pp. 718–722, Apr. 2017, doi: 10.1111/1471-0528.14305.
- [4] L. Thurn, A. Wikman, and P. G. Lindqvist, "Postpartum blood transfusion and hemorrhage as independent risk factors for venous thromboembolism," *Thromb Res*, vol. 165, pp. 54–60, May 2018, doi: 10.1016/j.thromres.2018.03.002.

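### The primary outcome is a difference in mean haemoglobin drop, but the protocol leaves open a Mann-Whitney test, which neither tests nor estimates that difference

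*Protocol*

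**What the plan says.** Under Outcome measures, the protocol gives the primary outcome as "Decreased mean hemoglobin drop after cesarean delivery at the Calcium gluconate arm, compared to the control arm". The PICO statement just above it also refers to a mean.

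The Analysis Plan sizes the trial on a mean. The cited study "demonstrated an average blood loss of 1.05 g/dL in 1000 women" (called blood loss, but in haemoglobin units), and the plan goes on: "Assuming a reduction in blood loss of 30% attributed to both coagulative effect and uterotonic effect of Calcium". It concludes that "a sample size of 1180 patients (590 in each arm) is needed to achieve power of 0.8 and p-value <0.05", after allowing for 10% dropout.

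On tests, the same section says: "Continuous variables will be compared using the student's t-test or Mann-Whiteny test". It gives no rule for choosing between the two and no separate primary analysis. The only model mentioned has another target: "a multivariate model will be built to assess the effect of calcium supplementation on postpartum hemorrhage". It therefore does not supply the mean difference.

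**The concern.** Outcome and sample size are both expressed as means, and one of the two permitted tests does not concern means. Mann-Whitney asks whether a value from one arm tends to exceed a value from the other. It yields no difference in g/dL, and it can disagree with the mean when the arms differ mainly in a tail.

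Two things are at stake. First, the reported p-value could belong to a different question from the stated outcome, with no matching effect estimate. Second, two open tests for one primary outcome allow the choice to be made after the data are seen, which raises the false-positive rate.

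The rank test is not needed for validity. With about 531 evaluable women per arm, a comparison of means does not depend on normally distributed data.

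**Working it through.** **Inputs from the protocol.** Control mean 1.05 g/dL; planned reduction 30%, so 0.30 × 1.05 = 0.315 g/dL; 590 per arm; 10% dropout, so 590 × 0.9 = 531 evaluable per arm; power 0.80; alpha 0.05, taken as two-sided because the side is not stated.

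**The plan's own figure.** The total of 1180 cannot be reproduced independently, because no SD is given. Solving n = 2(1.96 + 0.842)² SD² / 0.315² for n = 531 gives an SD of about 1.83 g/dL. Putting 1.83 back gives 530 per arm, 1060 in total, and 1060 / 0.9 = 1178 after dropout. That agreement is circular. Other SDs give totals of 354 (SD 1.0), 507 (SD 1.2) and 792 (SD 1.5).

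**Uniform shift of 0.315, normal data, SD 1.83.** The standard error is 1.83 × √(2/531) = 0.1123, and 0.315 / 0.1123 = 2.80. The t-test power is Φ(2.80 − 1.96) ≈ 0.80. For normal data the relative efficiency of Mann-Whitney is 3/π = 0.955, so its power is about Φ(2.80 × √0.955 − 1.96) ≈ 0.78. Simulation gives 0.79 and 0.77.

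**An assumed skewed population.** Suppose 90% of control women drop N(0.85, SD 0.8) and 10% drop N(2.85, SD 1.2).
- Mean: 0.9 × 0.85 + 0.1 × 2.85 = 1.05.
- Variance: 0.9 × 0.64 + 0.1 × 1.44 + 0.9 × 0.1 × 2² = 1.08, so SD 1.04.
- Halving the heavy share to 5% lowers the mean by 0.05 × 2 = 0.10 g/dL.

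Simulated power at 531 per arm, two-sided 0.05, women treated as independent:

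| Effect in this population | t-test | Mann-Whitney |
|---|---|---|
| Uniform shift 0.315 (planned size) | 0.998 | 0.999 |
| Heavy share halved plus shift 0.215 (total 0.315) | >0.999 | >0.999 |
| Heavy share halved plus shift 0.10 (total 0.20) | 0.91 | 0.84 |
| Uniform shift 0.15 | 0.66 | 0.74 |
| Heavy share halved only (0.10) | 0.37 | 0.22 |

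Check of the last t-test figure: with a 5% heavy share the variance is 0.95 × 0.64 + 0.05 × 1.44 + 0.95 × 0.05 × 2² = 0.87. The standard error is √((1.08 + 0.87)/531) = 0.0606, and Φ(0.10/0.0606 − 1.96) ≈ 0.38.

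**The planned 0.315 coming wholly from heavy bleeders.** Here 5% to 20% of women have an added gamma-distributed excess over a normal bulk of SD 0.7 to 1.0, and calcium shrinks only that excess. The t-test has power 0.95 to 1.00 and Mann-Whitney 0.27 to 0.79. These settings are extreme. With 5% heavy bleeders the mean excess must be 0.315 / 0.05 = 6.3 g/dL and must be abolished. With 10% it is 3.15 g/dL, also abolished. With 20% and a mean excess of 2.5, the reduction is 0.315 / (0.20 × 2.5) = 63% of the excess.

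**Choosing after seeing the data.** With no effect, each test alone holds 5% in the skewed population. Taking the smaller p-value gives 5.6% for normal data and 6.7% for the skewed population (10,000 trials; repeat runs of the latter gave 6.5% and 6.9%).

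**The case against.** The strongest reply is that the sentence is generic. It also covers length of stay, duration of surgery and estimated blood loss, which are often skewed and for which Mann-Whitney is reasonable. It does not assign that test to the primary outcome, and both the outcome definition and the sample size point to the t-test. Choosing between two standard tests is something a statistical analysis plan commonly settles. This stands in part: harm arises only if Mann-Whitney is used for the primary, or if the choice follows the data. It does not remove the point, because the protocol itself states the permitted tests, makes no exception for the primary, and one of them is off target.

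A reader might infer that the plan is set to miss a real benefit. The documents do not support that. They attribute the effect to clotting and to uterine contraction together, and nowhere say that only heavy bleeders gain. In the assumed population above, removing every heavy bleeder lowers the mean by only 0.10 × 2 = 0.20 g/dL, so the planned 0.315 could not be a pure tail effect there. In the tail-only case of 0.10 g/dL the t-test itself fails 63% of the time, so naming it would not rescue that trial.

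A reader might also infer that a normality test will push the analysis to ranks. In the assumed skewed population such a test rejects in essentially every trial, but the protocol mentions no such trigger.

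Finally, a secondary outcome, "The rate of women with a decrease of hemoglobin levels of 2 gr/dl or more", looks directly at large drops. In the 0.10 g/dL tail-only case a chi-square test on it has power 0.38, much like the t-test. That mitigates, but it is not the primary analysis.

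**Conclusion.** The mismatch is real and lies in the stated text: a primary outcome and sample size built on means, and an analysis sentence that also permits a test that does not address means. It should be corrected, but its measurable size is modest. The false-positive rate would be about 6% to 7% rather than 5%, and only if the smaller p-value were taken, which nothing in the protocol says will happen.

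Power is not the main argument. At the planned effect as a uniform shift the tests are almost equal. Mann-Whitney is clearly weaker only under a tail-concentrated benefit, and it is stronger for a shift of 0.15 g/dL in the skewed population. The case for fixing the test is agreement with the stated outcome.

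The SDs, heavy-bleeder shares and distribution shapes are assumptions, because the protocol gives none. All the simulations ignore the allocation by calendar month, so they compare the two tests and do not give the trial's true power.

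**What to change.** State one primary analysis in the Analysis Plan: the difference between arms in mean haemoglobin drop with a 95% CI, from a method for means (for example a linear model), whatever the shape of the data. The standard errors must respect the month-based cluster allocation described under Research arms and randomization; robust errors that treat women as independent would not. Keep Mann-Whitney for skewed secondary variables and, for the primary outcome, only as a labelled sensitivity analysis.

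This costs one sentence and changes nothing in conduct or data collection. The small downside is some loss of power if the true effect is a pure shift in a heavy-tailed distribution (0.66 against 0.74 in the 0.15 g/dL example).

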- 2. The need for additional therapy for the management of PPH
- 3. Receipt of blood products.
- 4. Patients treated with intravenous ferrous (iron).
- 5. The estimated blood loss during the surgery.
- 6. Hospitalization length of stay.
- 7. Duration of cesarean delivery.
- 8. A composite of adverse maternal outcomes including at least one of the following: admission to intensive care unit (NICU), the need for a surgical treatment for uncontrolled PPH, massive blood transfusion (defined as transfusion of ≥10 units red blood cells (RBCs) in 24 hours, disseminated intravascular coagulation (DIC), and death.
- 9. Endometritis or antibiotic treatment following CD.

PROPOSED TRIAL

Design: Multi Center (Rambam Health Care Campus, Soroka Medical Center), clusterrandomized, double-blind controlled trial.

Eligibility criteria for participants:

We plan to conduct a randomized control trial of all women undergoing elective cesarean delivery.

Inclusion criteria:

1. Gestational age of 35 weeks or more.

Exclusion criteria:

- 1. Age younger than 18 years old.
- 2. Patients treated with calcium channel blockers.
- 3. Chronic renal failure and hyperphosphatemia.
- 4. Sarcoidosis.
- 5. Hypocalcemia (ionized Ca<1 mmol/L) or hypercalcemia (ionized Ca> 1.3 mmol/L) before the surgery.
- 6. Any QT abnormalities as evident by ECG before Calcium Gluconate administrations or any known conduction abnormality.

Research arms and randomization:

After signing a consent form prior to the surgery (at the pre-operative assessment), At the third stage of labor, women who gave their consent to participate in the study will get either 10 ml of Calcium Gluconate 10% solution (containing 0.94 gr of calcium gluconate) diluted in 100 ml of normal saline IV or 110 ml of normal saline IV.

The solutions will be given in addition to Carbetocin (a long acting oxytocin analogue), in both arms.

We will use calcium gluconate during even-numbered months and normal saline during oddnumbered months, or vice versa, according to randomization that will be known to the primary researcher alone.

A blood sample will be drawn at the beginning of the surgery and sent for blood gas analysis, determining ionized calcium levels and coagulation profile. Women with hypocalcemia or hypercalcemia will be excluded from the trial. Only patients with normal calcium levels between 1.0-1.3 mmol/L will be included in this trial.

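### The primary hemoglobin drop gets an unadjusted patient-level test despite allocation by month, while the one multivariable model is aimed at an undefined, unlisted outcome

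*Protocol*

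**What the plan says.** - **Outcome.** Under Outcome measures, the protocol gives one primary outcome: "Decreased mean hemoglobin drop after cesarean delivery at the Calcium gluconate arm, compared to the control arm". Nine secondary outcomes follow.
- **Allocation.** The Design paragraph calls the study a "clusterrandomized, double-blind controlled trial". Under Research arms and randomization the unit is the calendar month: "We will use calcium gluconate during even-numbered months and normal saline during oddnumbered months, or vice versa, according to randomization".
- **Hemoglobin data.** The same section has a blood count taken the next day and compared with the level before surgery. Pre-operative Hb is therefore in hand for every woman with a primary outcome.
- **Analysis.** The Analysis Plan assigns tests by type of variable and then turns to one model: "t-test or Mann-Whiteny test. After testing for collinearity, confoundment and interaction, a multivariate model will be built". The target of that model is postpartum hemorrhage (PPH): "a multivariate model will be built to assess the effect of calcium supplementation on postpartum hemorrhage".
- **PPH elsewhere.** The Hypothesis mentions it as a possible benefit: "thus has the potential of reducing the incidence of PPH and its complications". Among the secondary outcomes it appears only through its treatment: "The need for additional therapy for the management of PPH" (item 2) and, as one component of the composite, "the need for a surgical treatment for uncontrolled PPH" (item 8).

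**The concern.** Two things do not fit together.

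First, the stated method for the primary outcome does not match the design. A t-test or rank test on individual women treats them as independent. When whole months receive one treatment, anything else that makes the Hb drop vary from month to month enters the comparison of arms. A patient-level standard error leaves that out, so it would be too small wherever such variation exists. The plan also leaves a t-test and a rank test as alternatives, although the outcome is a mean and a rank test does not estimate a difference in means.

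Second, the one adjusted analysis is spent on an outcome outside the protocol's own list. A fall in Hb of 2 g/dL or more, estimated blood loss and treatment for PPH are different quantities, and the protocol does not say which of them, if any, stands for PPH. The adjusted result would then answer a question that the outcome list does not ask, while no model is named for the primary outcome.

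**Working it through.** **Outcomes against analyses**

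| Quantity | Listed as an outcome? | Analysis stated |
|---|---|---|
| Mean Hb drop | Primary | General t-test or Mann-Whitney sentence |
| Hb fall of 2 g/dL or more | Secondary 1, not labelled PPH | General chi-square or Fisher sentence |
| Additional therapy for PPH | Secondary 2 | General chi-square or Fisher sentence |
| Estimated blood loss | Secondary 5, no cut-off | General t-test or Mann-Whitney sentence |
| Severe-outcome composite | Secondary 8; PPH is the reason for one component | General chi-square or Fisher sentence |
| Occurrence of PPH | Not listed; no blood-loss, Hb or time criterion | The multivariable model |

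**The plan's own figure.** The assumed control drop is 1.05 g/dL and the reduction 30%, so the target difference is 0.30 × 1.05 = 0.315 g/dL. The total is 1180; less 10% dropout, 1180 × 0.9 = 1062 evaluable women, or 531 per arm. No SD is stated, so 1180 cannot be reproduced from its inputs. Solving backwards with two-sided alpha 0.05 (sidedness assumed) and power 0.80 gives SD = 0.315 × √(531/2) / 2.802 = 1.83 g/dL. This shows only which SD a comparison of individual women would imply. It is not used below.

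**What pre-operative Hb adds as a covariate.** Let pre- and post-operative Hb have equal SD s and correlation r (both are assumptions; the protocol gives no r).

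- Variance of the drop: 2s²(1 − r)
- Residual variance of next-day Hb after adjustment for pre-operative Hb: s²(1 − r²)
- Ratio: (1 − r²) / [2(1 − r)] = (1 + r)/2

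| Assumed r | Variance ratio | SE factor (square root) | SE reduction |
|---|---|---|---|
| 0.5 | 0.75 | 0.866 | about 13% |
| 0.7 | 0.85 | 0.922 | about 8% |
| 0.9 | 0.95 | 0.975 | about 3% |

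These are individual-level figures. Variation between months is outside them, so they do not translate into power.

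**What allocation by month costs.** The protocol does not give the number of months. With k months in all and a month-level comparison on k − 2 degrees of freedom, the multiplier for a 95% CI replaces 1.960:

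| Assumed months | df | t multiplier | Divided by 1.960 |
|---|---|---|---|
| 12 | 10 | 2.228 | 1.137 |
| 18 | 16 | 2.120 | 1.082 |
| 24 | 22 | 2.074 | 1.058 |

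So the interval is 14%, 8% or 6% wider than a patient-level one from the same model, before any between-month variance is added. At the middle assumptions the two effects roughly cancel: 1.082 × 0.922 = 0.998. The case for the model is therefore a valid standard error first, and precision second.

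**The case against.** The strongest reply is that much of this belongs to a statistical analysis plan that may exist but is not at hand: which covariates to adjust for, how PPH is defined, whether a rank test is a sensitivity analysis. That stands for missing detail, and none of it is held against the protocol as an omission. It does not cover what the protocol does state: a test that takes no account of its own allocation unit, and a model target absent from its own outcome list.

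A second reply is that PPH is loose shorthand for the bleeding outcomes. The Analysis Plan itself calls a 1.05 g/dL figure blood loss, so this is possible. It still leaves several non-equivalent candidates, and the wording needs settling.

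Some stronger readings are tempting and are not supported:

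- *The plan discards pre-operative Hb, or is invalid without covariates.* The drop already subtracts pre-operative Hb. Only the residual gain shown above is lost, and lack of covariates alone does not invalidate the comparison.
- *Covariates will be selected from the trial data.* Testing for confounding and interaction suggests it, but no selection rule is stated, and checking collinearity is not selection on outcome.
- *The primary outcome will never receive an adjusted estimate.* The protocol names none, but does not exclude one.
- *Adjustment would raise power from 0.80 to some higher figure.* That would need the back-solved SD, an assumed r and no variation between months.

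**Conclusion.** The point holds as a mismatch between design, outcome and analysis. The primary Hb drop is assigned an unadjusted test of individual women although months are allocated, and the one multivariable model addresses an outcome that is neither defined nor listed.

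The loss from not using pre-operative Hb as a covariate is modest, about 3% to 13% of the individual-level standard error for assumed correlations from 0.9 down to 0.5 with equal SDs. The effect of ignoring months has a known direction (intervals too narrow), but its full size cannot be given: the documents state neither the number of months nor the between-month variance. The target of the multivariable model is a textual discrepancy with no figure attached. It affects a supporting analysis rather than the primary test. The change should be made, because a better method than the stated one is available for little more than wording.

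**What to change.** 1. State the primary analysis as a linear model of next-day Hb (or the Hb drop) on arm, with pre-operative Hb and site as covariates fixed in advance. Report the adjusted mean difference with a 95% CI whose standard error reflects allocation by month, for example a random month effect with small-sample degrees of freedom.
2. Keep any rank test of the primary outcome as a sensitivity analysis.
3. Point the multivariable model at the primary outcome. Alternatively, define PPH and add it to the secondary outcomes.
4. Let the prespecified covariates take the place of the testing for confounding and interaction.
5. Do not extend multivariable modelling to rare secondary outcomes such as the composite, where few events may prevent a stable fit.

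**Cost.** Plan wording, and two extra coefficients with about 1062 evaluable women. If PPH is kept, it needs a definition and data to support it. The month-aware interval will be wider than the patient-level one, by the factors shown above plus whatever between-month variance exists. That width comes from the design, not from the covariates.
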